### **Sample #3**

Specify subject population

Initial pilot study participant peer health advocates "seeds"

Number of completers required to accomplish study aims

16

Projected number of subjects who will be enrolled to obtain required number of completers  
18

Age range of subject population

18-25

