## Specific Aims and Hypotheses

*Concisely state the objectives of the study and the hypothesis or primary research question(s) being examined. There should be one hypothesis for every major study procedure or intervention. For pilot studies, it is important not to overstate the study's objectives. If there are no study hypotheses, describe broad study goals/aims.*

The specific aims of this study are

1. **Formative Work:** To inform intervention development through
  - a. Focus groups (six eight) with at-risk AGYW aged 18-25, grouped by age and recruitment venue (community, family planning clinic) to explore knowledge of, beliefs about, motivators for, and concerns about PrEP in the context of gendered relationship dynamics and PrEP-related stigma;
  - b. Qualitative interviews with 10 Focus Group participants to obtain more in-depth and individually-focused understanding of topics discussed in the Focus Groups.
  - c. Qualitative interviews with men (10 HIV-positive and 10 HIV-negative or unknown status) who have female partners aged 18-25 to understand men's views of PrEP and of their partners' use of PrEP.
2. **Intervention development (revised):** To develop—in collaboration with a working group of at-risk AGYW—develop a virtual group-based Gender-Enhanced PrEP Information-Motivational workshop, drawing on our formative data and strategies from our prior HIV prevention interventions; and to choose a PrEP video and a PrEP informational website for the individual digital access control condition.
3. **Pilot (revised):** To evaluate acceptability, feasibility, and outcomes of the intervention components:
  - a. Workshops: Compare participants (N=98 100) randomized to the virtual group interactive workshop with those randomized to individually-accessed links to a PrEP promotional video and PrEP information on the *primary outcome* of having an individual discussion with the study nurse about the possibility of taking up PrEP; undergoing HIV self-testing guided by the study nurse (either in-person at the GHRU office or via telehealth visit) (*secondary outcome*); if eligible for PrEP, initiating PrEP (*secondary outcome* and *hypothesized mediators* (risk perception, gender barriers, self-efficacy, outcome expectancies, PrEP-stigma,

peer norms, information) post-intervention and at 3-months;

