**Pilot Study: Gender-enhanced (GE) virtual interactive group vs Individually-Accessed (IAO) activities Workshop for women**

**Recruitment and screening.** Recruitment of initial workshop Peer Health Advocates (PHAs). Trained Staff will directly recruit an initial group of **16** women (“seeds”) with the help of Addington Gateway clinic staff and IDWG participants, who will provide study information to potential participants through flyers. Interested women will contact study staff to be screened for eligibility or be screened on the spot. We anticipate screening 30 women to identify 16 seeds. Seeds will be randomized to attend either the virtual group-based Gender-Enhanced (GE) workshop or the individually-accessed (IA) weblink only material. Women eligible at this step will meet the same eligibility criteria described above, and, additionally, will *be willing to speak with others in their networks about HIV prevention and invite them to attend the workshop (i.e., to become Peer Health Advocates [PHAs]).* They will not have been FG members. We will ensure that women from the two age groups are included and will stratify by age before randomizing them to participate in the GE workshop or IA material. This group (the seeds) comprises both Wave 1 attendees and Wave 1 PHAs.

[figure not shown]

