Subsequent recruitment. Subsequent PHAs (Waves 2-4) will be drawn from workshop attendees (who do not have to agree to be PHAs), and their numbers will be supplemented if needed using Wave 1 recruitment procedures. At the end of a workshop (or, for IA participants, after viewing the online materials), study staff will invite all participants to become PHAs and to reach out to their network members to help them prevent HIV infection. PHAs will invite network members to participate in the activity (GE or IA) they, themselves, participated in (and will inform them that brief assessments are included). We will repeat this process three more times, for a total of four recruitment “waves” (see Table below). We expect that the initial PHAs (n=16, Wave 1) will refer 28 workshop attendees. Of these 28, we expect at least 50% will agree to be PHAs (Wave 2). These 14 will average two referrals (n=28) who are eligible and participate. We expect half of participants to agree to be PHAs (Wave 3), through a total of four waves. If we fail to enroll 14 new PHAs from the pool of attendees, we will add new recruits, as for the initial seeds. We expect each wave will take approximately two months. To attain a target **98 100** participants attending and completing Waves 2 through 4, we anticipate that we may need to enroll up to 120 women.

Peer-driven recruitment waves and follow-up N = 100 <del>98</del> 100	Wave 1 (seeds)	Wave 2	Wave 3	Wave 4 (if need ed)	
Study Months					
Wave 1: Seeds randomized (1:1) to attend GE or IA condition  Workshop (WS)	16				
Wave 2: Recruitees who participate attend WSs		28 14			
WS Attendees who become PHAs					
Wave 3: Recruitees who participate attend WSs			28 14		
WS attendees who become PHAs					
Wave 4: Recruitees who participate attend WSs				28	
WS Attendees who become PHAs					
Total Attendees/wave (N= 98 <del>100</del> )	16	28	28	28 <del>30</del>	
Follow-up interviews		16	28	28	28

[figure not shown]

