flowcharts (Figure 1 & 2) for seeds and subsequent participants, respectively. Following wave 1 (seeds) (who will be recruited directly by study staff), potential participants will contact study staff by telephone. Women will send their recruitment coupon and official identification to verify age on an online platform, WhatsApp®. Eligibility criteria will be assessed telephonically, using a scripted eligibility screener preceded by verbal consent for eligibility screening. A copy of the study Informed Consent form will be sent to the participant and reviewed with her. The consenting procedure will be conducted telephonically and will be audio-recorded to document the participant's verbal consent. Potential participants will be told that the study includes (1) a pre- and post-intervention questionnaire; (2) GE: online activities prior to and after the group session and 1 online interactive-group workshop of 90 minutes; IA: being sent links to PrEP and contraceptive information and to a PrEP video; and (3) a 3-month follow-up **survey, with some participants selected for an interview**. After consenting, participants will complete a self-administered questionnaire.

**Conduct of workshops.** Both the GE and IA interventions will be conducted via WhatsApp, in English (and Zulu) by bi-lingual study staff. The GE workshop will begin with several assignments that are conducted asynchronously (i.e., participants are sent materials for an activity that they conduct on their own), followed by a 90-minute synchronous (i.e., in real time) interactive group session. To avoid contamination, PHAs will recruit only for the online condition they attended. In the GE condition a maximum of six attendees/workshop group is ideal; the minimum number of women needed to run a workshop will be four. Therefore, based on a sample of ~100, with ~50 in the GE condition, we expect to conduct 8-12 online GE workshop groups. In the IA condition, women will be sent the links for the online intervention materials as soon as they have completed the pre-intervention assessment. They can access and review these materials whenever they want. Women in both conditions will receive R200 R250 (~\$17.00) for completing the intervention and assessments. R50 will be given immediately upon

enrolling, so that women will be able to pay for mobile phone airtime to access the materials; the remainder will be given upon completion of the post-intervention assessment.

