## Data Analysis

Workshops: Compare women randomized to the virtual group-interactive workshop with those randomized to individually-accessed links to a PrEP promotional video and PrEP information on the **primary outcome of having an individual discussion with the study nurse about the possibility of taking up PrEP; undergoing HIV self-testing guided by the study nurse (either in-person at the GHRU office or via telehealth visit) (secondary outcome); if eligible for PrEP, initiating PrEP (secondary outcome)**, and, for all women, changes in hypothesized mediators (information, risk perception, gender barriers, outcome beliefs, PrEP-stigma, peer norms) post-intervention and at 3-month follow-up.)

To compare the **primary and secondary outcomes** across the two workshop conditions, we will use generalized linear models (GLM) with a logit link function and the method of generalized estimating equations (GEE) to account for the effect of clustering within recruitment chain. The logit link function is appropriate because the primary and secondary outcomes are dichotomous and characterized as yes/no if achieved at any time over the course of the study by the time of the 3-month follow-up interview. Intervention condition (Gender-Enhanced or Individual Access) is the primary predictor. Although the original data analysis plan also specified accounting for clustering by workshop group attended, we will not account for clustering by workshop group because women in the IA condition received the intervention as individuals rather than as groups.

We will adjust for any substantial baseline differences by condition on age. We will also adjust for any substantial differences by other demographic and behavioral characteristics, such as education level, whether attending school, has a primary partner, sexual risk behaviors (to be defined), relationship power, reported intimate partner violence if these factors differ substantially by condition at baseline and are also associated with the outcome (i.e., meet the conditions of confounding).

To assess if being a PHA, i.e., talking to other women about HIV prevention serves as an additional intervention dose, a secondary analysis will include a variable for whether the woman served as a PHA and recruited other workshop attendees (yes/no).

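### Only the seeds are randomised, so the arms are compared across about 16 recruitment chains; the SAP names no small-sample method for its chain-clustered GEE, and its power figure states no number of chains

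*SAP*

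**What the plan says.** **Allocation.** The protocol's Pilot Study section (Recruitment and screening) plans 16 seeds and states: "Seeds will be randomized to attend either the virtual group-based Gender-Enhanced (GE) workshop or the individually-accessed (IA) weblink only material". Staff "will stratify by age before randomizing them to participate in the GE workshop or IA material". For everyone after the seeds, Subsequent recruitment says "PHAs will invite network members to participate in the activity (GE or IA) they, themselves, participated in", and Conduct of workshops adds "To avoid contamination, PHAs will recruit only for the online condition they attended".

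**Number of chains.** Sample #3, labelled "Initial pilot study participant peer health advocates", requires 16 completers and projects 18 enrolled. Subsequent recruitment also allows a top-up: "If we fail to enroll 14 new PHAs from the pool of attendees, we will add new recruits, as for the initial seeds". It does not say how many would be added.

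**Description.** Specific Aim 3a compares participants "randomized to the virtual group interactive workshop with those randomized to individually-accessed links". The SAP's revised Aim 3a and its Data Analysis section likewise speak of randomised women.

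**Analysis.** The SAP's Data Analysis section uses a logit model and "the method of generalized estimating equations (GEE) to account for the effect of clustering within recruitment chain". It drops clustering by workshop group and allows covariate adjustment. It names no variance estimator, small-sample correction, reference distribution or working correlation, and it does not define a chain by its originating seed.

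**Test and power.** SAP Power Considerations plans a two-sided 0.05 test and 95% intervals to rule out unusually large or small effects. It claims 80% power at 33-36 points with 100 women, control rates of 20-50% and a within-cluster correlation of at most 0.1. It gives no number or size of clusters, and says that testing is not the pilot's primary goal.

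**The concern.** Arm is constant within a chain, so the independent units are the chains, about eight per arm as planned. The robust sandwich is justified as the number of clusters grows. With about 16 it tends to understate the variance, and a normal reference adds to the problem. A SAP that says only GEE leaves the software default open, and that default is commonly the uncorrected version.

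At stake are the p-value and effect interval for the primary comparison, the power statement, and the description of the trial. By the protocol's wave table, 28 + 28 + 28 = 84 of 100 women enter an arm already fixed by their recruiter. A reader told that 100 women were randomised would credit the comparison with more independent allocation than it has.

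**Working it through.** **1. Inputs.** 16 seeds at 1:1, 100 women in total (16 + 28 + 28 + 28), at most 3 recruits per advocate (protocol, Pilot Study). Two-sided alpha 0.05, correlation 0.1, control rate 20-50% (SAP, Power Considerations). Mean chain size m = 100/16 = 6.25.

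**2. The SAP's own figure.** With design effect DE = 1 + (m - 1) x 0.1 and n = 50/DE per arm, solve d x sqrt(n) = 1.96 x sqrt(2 x pbar x (1 - pbar)) + 0.842 x sqrt(p0(1 - p0) + p1(1 - p1)), where p1 = p0 + d and pbar is the mean of p0 and p1, over control rates 20-50%.
- m = 8: DE = 1.70, n = 29.4, d = 33.7-35.8 points.
- m = 6.25 (16 chains): DE = 1.525, n = 32.8, d = 32.2-34.0 points.

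So 33-36 points is what a large-sample normal calculation gives with a mean cluster size near 8. The SAP does not state the size it used. The range reflects how the detectable difference varies with the control rate.

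**3. Error rate and coverage at 16 chains.** These come from simulation: beta-binomial outcomes, 8 versus 8 chains, logit GEE clustered on chain, 6,000 to 20,000 replicates per setting. Chains were either near-equal (6-7 women) or grown by the protocol's wave rules (size CV about 0.66). Ranges span repeated runs at correlation 0.1.

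| | Near-equal chains | Wave-grown chains |
|---|---|---|
| Null rejection, uncorrected sandwich with z | about 8% | about 10-11% |
| Coverage of its nominal 95% interval | about 92% | about 89-90% |

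Small-sample corrections gave null rejection of about 3-6% and coverage of about 94-96%. One run had Kauermann-Carroll with t(14) at up to 6.4% in wave-grown chains. A permutation test of seed allocation (4,000 replicates) gave 3.9-4.7%. With covariates in the model, the uncorrected test rejected 8.3-10.6% (equal) and 10.6-12.6% (uneven).

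**4. More chains.** Over correlations 0-0.1, uncorrected null rejection was 8.2-10.6% with 18 seeds, 7.3-8.6% with 24 chains and 5.9-7.4% with 30.

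**5. Detectable difference at 80% power, 16 near-equal chains, correlation 0.1.**

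| Test | Control 20% | 35% | 50% |
|---|---|---|---|
| t-test on chain proportions | 34.5 | 36.0 | 33.5 |
| Mancl-DeRouen with z | 35.4 | 36.7 | 34.5 |
| Kauermann-Carroll with t(14) | 36.0 | 37.3 | 35.0 |

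The first roughly meets 33-36. The second exceeds the upper end by under a point (36.7 against 36). The third misses by 1-2 points; a separate set of runs gave 35-38.

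**6. Uneven chains.** Power with the difference matched to the control rate, near-equal then wave-grown:

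| Test | 33 points, control 50% | 36 points, control 35% |
|---|---|---|
| t-test on chain proportions | 78.7%, 63.3% | 80.4%, 65.3% |
| Mancl-DeRouen with z | 76.3%, 70.2% | 78.5%, 72.8% |
| Kauermann-Carroll with t(14) | 74.4%, 70.1% | 77.1%, 72.7% |

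With wave-grown chains all three miss. For Kauermann-Carroll with t(14) the detectable difference becomes about 37-40 points. With uneven chains it falls to 36-39 points for 18 seeds, 34-36 for 24 chains and 32-34 for 30 (99 women in the last two), so the SAP's range is met from about 24 chains.

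**The case against.** The best case for the plan has four parts.

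- **It is a pilot.** The SAP says that testing is not the primary goal and that power will generally be insufficient. The illustration for the later trial is sized on an extrinsic 15-point difference. This stands, and it limits the severity. It does not rescue intervals meant to rule out effects, nor the interval estimates that the SAP says will accompany its tests.
- **The power text is inherited.** It comes from the original proposal and refers to a comparator and outcome since replaced. That is true, but it remains the SAP's only power statement.
- **Sixteen chains is not fixed.** Eighteen seeds are projected and top-ups are allowed. This stands for power. It only partly answers the error rate, which stayed above 5% even at 30 chains. Parts of the SAP are written after the intervention was delivered, so the actual number of chains can probably be counted.
- **Part of the interval wording concerns simple means and proportions**, for which exact binomial intervals are named. That is fair; the problem applies to the GEE contrast.

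Two stronger readings are tempting. A reader might infer that the SAP has chosen an uncorrected sandwich; it has not, and the risk comes from its silence. A reader might also infer that the true detectable difference is 35-38 points and not 33-36. That is one method's result with near-equal chains. A valid chain-level t-test roughly reaches the stated range, and the SAP does not promise 80% power at 33 points for every control rate.

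**Conclusion.** The point holds as a specification gap that should be fixed. The comparison is cluster-randomised by originating seed. With about 16 chains, the usual default would turn a 5% test into one of about 8-11% and a 95% interval into one of about 89-92%. The stated power is neither simply right nor simply wrong: at 16 chains and correlation 0.1 it depends on the test and on how uneven the chains are, and with about 24 or more chains it is met.

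Assumptions not in the documents are the chain-size distribution, beta-binomial outcomes, correlation at its stated limit (a lower value raises power), and, for the 24- and 30-chain cases, extra randomised seeds added in two waves. Clustering by workshop within the GE arm was not modelled. The protocol's Figures 1 and 2 were not available; no text that could be read randomises a woman after the seeds.

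**What to change.** 1. State in both documents that the seed's chain is the randomised unit. Define each chain by its originating seed, including supplementary seeds, and report randomised chains per arm beside the number of women.
2. Pre-specify one small-sample method for all GEE p-values and 95% intervals, including the covariate-adjusted models. Candidates are a Mancl-DeRouen sandwich, a Kauermann-Carroll sandwich with t on degrees of freedom based on the number of chains, or a permutation test that re-randomises seeds within the age strata. Name the working correlation.
3. Restate the detectable difference for that test and for the planned or actual number and sizes of chains, as a conditional figure.

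The cost is a few sentences and a software option, with no change to enrolment. Intervals widen by about 14-22% at 16 chains and 9-10% at 30, and the stated detectable difference may be up to a few points less favourable.

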Initial Pilot Study participants, who agree to be Peer Health Advocates (PHAs) (“seeds”)		
CRITERION	METHOD OF ASCERTAINMENT	
Inclusion:		
1. The first 16 ‘seed’ PHAs will not have been Focus Group participants and will be required to agree to be PHAs before participating in the pilot study. This involves being willing to speak with others in their networks about HIV prevention and invite them to participate in the virtual interactive group-workshop or the individually-accessed weblink materials. (All other attendees will not be required to agree to this before participating, and it will be optional for them to decide on whether	Completion on a computer “tablet” of screening questions or via pencil and paper if desired or via interview by trained bi-lingual staff if needed (illiterate).  Proof of age will be required at workshop attendance.	

or not to become a PHA.) Other eligibility criteria are identical to those for the Pilot Study:
 
 
1. Aged 18-25
 
2. self-reported HIV-negative or unknown status
 
3. heterosexual vaginal or anal intercourse reported in the past 6 months <del>if aged 18-25</del>
 
4. presently residing in eThekweni-metropolitan Durban;
 
5. has private internet access
 
6. Is not currently taking PrEP or planning to begin
 
7. Conversant in isiZulu or English
 
8. Willing to be audiotaped as a Pilot study participant
 
		

Exclusion:
 
 
1. Obvious signs of cognitive impairment
 
2. Was a FG participant
 
	
 
1. Trained bi-lingual staff will assess based on participant presentation.
 
2. Study records
 
	

Pilot Study participants, recruited by PHAs to the virtual interactive-group Gender-enhanced (GE) or Individually-Accessed weblink Information-only (IAO) Activities Workshop for women
		

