In total, we expect that **98** ~~100~~ women will attend and complete the intervention and assessment activities. To balance recruitment chain size, PHAs will be allowed up to 3 recruitees. PHAs *will not* assess eligibility for workshop attendance, but they will be able to inform potential recruitees of age eligibility, that interactive groups will be audio-recorded, and that the intervention activities are for women *who have had sex*. PHAs will receive R100 (approximately

\$7.69) for each recruitee who is eligible and participates in the activities; they will be told that they will not be paid unless their recruitee is eligible for and completes the activities. To reduce the possibility of coaching, PHAs will be told that staff will confirm criteria; proof of age will be required, and the assessment will ask several questions about sexual activity that may reveal inconsistencies if the recruit was never sexually active. To reduce the possibility of coercion, in the eligibility screener we will ask recruitees how long they have known the PHA who recruited them and if they felt coerced in any way to attend. Any PHA found to be engaging in such behavior will be informed that she may no longer recruit and that she will not get paid for any recruitees who report her as their recruiter.

Procedures for Eligibility screening, informed consent, and study enrollment. Procedures are shown in the

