online intervention materials as soon as they have completed the pre-intervention assessment. These include a link for the PrEP information/motivational video that also is part of the GE workshop, and links for a SA government-sponsored PrEP information website and a government-sponsored contraceptive information website. These materials constitute what would ordinarily be available to women receiving information about PrEP in a clinic or by themselves on the web. Women will be able to access and review these materials whenever they want. Additionally, participants will be sent the IPV component described above, and will be given instruction for women who want to be PHAs, as described above.

Quality Control. All GE intervention sessions will be audio-recorded, with the recording serving as the basis for weekly supervision. Facilitators' reports, completed following each session, will indicate problems, unusual circumstances and difficult issues.

Post intervention activities (both conditions). Brief post-assessments will be conducted. As part of the post-assessment, women will be asked if they want to speak with the study nurse about PrEP and/or about anything else. Notifications will be sent to staff when anyone responds "yes"; the study nurse will be notified to make a counseling appointment with the woman. After the post-assessment, women who wish to become PHAs will be given recruitment coupons and literature. Contact information will be confirmed and appointments for 3-month follow-up assessments made.

PrEP clinical assessment. After completing the online intervention (either condition), women will be invited to undergo individual counseling to help them determine if they want to take up PrEP. The counseling will be conducted by the MRC-GHCU staff nurse (who is a trained HIV C&T counselor), either remotely using WhatsApp or at the MRC- GHCU Ridge Road Site, in a private space. If the participant wishes to take up PrEP, the nurse will conduct HIV counseling and testing (HCT). Counselling and, if chosen, HIV-testing (optional) will be conducted using the MRC Gender and Health Research Unit PrEP counselling and HIV-testing SOP. This SOP follows standard DOH guidelines and uses publicly available and approved HIV-self testing kits (OraQuick). If women wish to self-administer the HIV test from home, the nurse will be available for guidance in conducting the test and for counseling regarding the results.

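### The planned PHA 'dose' analysis credits nurse sessions requested before any peer recruiting to a self-selected, partly wave-determined role, so it can support only an exploratory association

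*SAP*

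**What the plan says.** **The analysis.** The SAP (Data Analysis) asks whether being a PHA works as a further dose of intervention, and answers it as follows: "a secondary analysis will include a variable for whether the woman served as a PHA and recruited other workshop attendees (yes/no". The same sentence stands in the SAP section carried over from the proposal. The outcomes are yes/no, met if achieved at any time up to the 3-month follow-up. Covariates are added only if they differ by condition at baseline (and, for those other than age, are also associated with the outcome). No term for wave or seed status, no time ordering and no caveat on interpretation are planned.

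**Time order.** In the protocol's pilot study procedures (post-intervention activities), the question whether a woman wants to speak with the nurse is part of the post-assessment. Then: "After the post-assessment, women who wish to become PHAs will be given recruitment coupons and literature". The SAP's December 2020 revisions say that a yes answer starts the contact that leads to the counselling session, and that the outcome is met when the session takes place. The protocol (PrEP clinical assessment) also lets women who decline at first speak with the nurse later.

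**Who can be a PHA.** Seeds "will be required to agree to be PHAs before participating in the pilot study" (Inclusion/Exclusion Criteria), and "This group (the seeds) comprises both Wave 1 attendees and Wave 1 PHAs" (pilot study, recruitment and screening). For later women the role is optional. On the number of waves: "We will repeat this process three more times, for a total of four recruitment" waves. The recruitment table marks Wave 4 as conditional on need and shows no PHAs drawn from it.

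**The concern.** A dose has to come before the response it is meant to produce. Here, a woman who asks for the nurse at the post-assessment has set the primary outcome in motion before she holds a coupon. If she then recruits a friend, her session counts in favour of a PHA effect.

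Two further features work against a dose reading:

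- In the middle waves the role is voluntary and taken up after the intervention. Interest in PrEP could lead a woman both to see the nurse and to recruit. The SAP adjusts for nothing that predicts PHA uptake.
- Seeds and last-wave women have little or no choice, so the variable is partly a marker of wave. Seeds also differ in kind, because staff recruit them directly while later women come through peers.

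At stake is what the pilot says about peer outreach. The protocol's lay summary says that promising approaches will be tested in a larger study, and a false dose effect could feed that judgement. In addition, once a post-allocation variable is in the model, the coefficient for condition is no longer the total effect of condition.

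**Working it through.** **1. Planned numbers.** The pilot study section gives: "We expect that the initial PHAs (n=16, Wave 1) will refer 28 workshop attendees". For Wave 2 it plans on half or more of those attendees, 14, taking on the role, with the same 28 and 14 for Wave 3 and 28 attendees in Wave 4.

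- Attendees: 16 + 28 + 28 + 28 = 100, which matches the SAP's N.
- Expected PHAs: 16 + 14 + 14 = 44; non-PHAs: 56.
- Women whose value is largely set by wave: 16 seeds + 28 in Wave 4 = 44 of 100.
- The SAP variable also requires a recruit. Since "PHAs will be allowed up to 3 recruitees", the seeds' 28 recruits need at least 28/3, so 10, seeds; between 10 and 16 seeds would score yes.

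The documents give no power, effect size or outcome rate by wave for this analysis. All rates below are assumptions.

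**2. Self-selection alone, true PHA effect zero.** Assume a 35% outcome rate in every wave, all seeds scored yes, all Wave 4 women scored no, and half of the 56 women in Waves 2–3 PHAs. In Waves 2–3, 0.35 × 56 = 19.6 women have the outcome and 36.4 do not.

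If 60% of the 19.6 are PHAs, that is 11.76. The other 28 − 11.76 = 16.24 PHAs are 44.6% of the 36.4.

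| | PHA, outcome | PHA, none | Non-PHA, outcome | Non-PHA, none |
|---|---|---|---|---|
| Seeds | 5.60 | 10.40 | – | – |
| Waves 2–3 | 11.76 | 16.24 | 7.84 | 20.16 |
| Wave 4 | – | – | 9.80 | 18.20 |
| All | 17.36 | 26.64 | 17.64 | 38.36 |

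- All waves: OR = (17.36 × 38.36)/(26.64 × 17.64) = 1.42.
- Waves 2–3 only: OR = (11.76 × 20.16)/(16.24 × 7.84) = 1.86.

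If 70% are PHAs (13.72, leaving 14.28, or 39.2% of the others):

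- All waves: OR = (19.32 × 40.32)/(24.68 × 15.68) = 2.01.
- Waves 2–3 only: OR = (13.72 × 22.12)/(14.28 × 5.88) = 3.61.

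The 60–70% and 45–39% figures apply within Waves 2–3. Over all 100 women they correspond to 17.36/35 = 49.6% against 26.64/65 = 41.0%, and 19.32/35 = 55.2% against 24.68/65 = 38.0%.

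**3. Wave differences alone, no self-selection.** Take outcome rates of 50/40/30% for Wave 1, Waves 2–3 and Wave 4.

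- PHAs: (8.0 + 11.2)/44 = 43.6%. Non-PHAs: (11.2 + 8.4)/56 = 35.0%. OR 1.44.
- Reversed gradient (30/40/50%): 16.0/44 = 36.4% against 25.2/56 = 45.0%. OR 0.70.
- Equal rates: OR 1.00.

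**4. Simulation of the planned model.** 600 trials per scenario; logit GEE with independence working correlation and robust standard errors; 16 chains with condition assigned by chain; base outcome rate 40%; true PHA effect zero. Shared motivation has a log odds ratio of 1 per SD on both the outcome and PHA uptake. One quarter of outcomes are assumed to be requested after the post-assessment. Entries are the median OR and the share of trials with a significant positive PHA effect (3.5% for the planned model when nothing is wrong).

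| Scenario | As planned | Wave-adjusted | Waves 2–3 only | Waves 2–3, no request at post-assessment |
|---|---|---|---|---|
| Waves differ (50/40/30%) | 1.48; 17% | 1.04; 3% | 1.04; 3% | 1.04; 2% |
| Shared motivation | 1.48; 20% | 2.00; 30% | 2.06; 29% | 1.92; 7% |
| Both | 2.08; 41% | 2.10; 30% | 2.11; 29% | 1.92; 7% |

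Letting only 75% of seeds score yes hardly changes the planned model under shared motivation (OR 1.50; 21%). In the last column the lower share of false positives comes mainly from the smaller sample, since the odds ratio stays well above 1.

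**The case against.** The strongest defence is that this is one sentence about a secondary analysis in a pilot whose SAP says that hypothesis testing is not its main goal. No decision rule uses the PHA coefficient, and the main condition model omits the term. That stands, and it limits the severity.

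Several stronger readings are tempting but are not supported by the documents:

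- *PHA activity always follows the outcome.* The outcome is the session, not the request. Women may approach the nurse later, and HIV testing and PrEP initiation come later still. Seeds agree to the role before they take part. A real dose effect is therefore possible; the planned model cannot separate it from reversed order or shared motivation.
- *The role is fully fixed for seeds and the last wave.* Seeds are fixed only on agreeing, because the variable also needs a recruit. All attendees are invited to become PHAs, Wave 4 may not be needed, and new direct recruits may top up later waves. That last-wave women score no is an inference from there being no later wave.
- *The wave structure inflates the effect.* It does so only if outcome rates differ by wave, and the documents give no such rates. The opposite gradient biases downward, and with self-selection alone the fixed waves dilute the false effect.
- *Restricting to Waves 2–3 cures the problem.* It removes only the wave artefact. On the same assumptions the odds ratio rises from 1.4–2.0 to 1.9–3.6.

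**Conclusion.** The concern holds in a limited form. As written, the analysis can report a dose effect where none exists, for two reasons that the documents establish: sessions requested before any PHA activity count as outcomes, and the role is self-selected after allocation in the waves where women have a choice. A possible third source is the link between role and wave.

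The size rests on assumption. With a 35% outcome rate and the stated selection in Waves 2–3, the false odds ratio is about 1.4 to 2.0. Wave differences alone, at assumed 30/40/50% rates in either direction, give about 0.7 to 1.4–1.5, so they could add to or subtract from it. With equal wave rates and no selection there is no bias.

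A reader might infer that the trial's main result is compromised. It is not: the primary comparison of conditions does not contain the PHA term. Only the condition coefficient in the secondary model loses its meaning as a total effect. The severity is minor.

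**What to change.** Amend the SAP wording for this analysis:

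1. Exclude women who asked for the nurse at the post-assessment, and count only sessions first requested after coupons were issued. The post-assessment answer identifies the women to exclude, and the protocol already tracks coupons and recruits.
2. Include wave and seed status (coding any directly recruited top-up women as such), or limit the analysis to women who had a later wave to recruit into. Adjust for PrEP attitudes, perceived risk and stage of change where these were collected at pre-test.
3. Report the result as an exploratory association, not a dose effect. Take the condition effect only from the model without the PHA term.

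Step 3 is essential. Step 1 removes reversed time order and step 2 the wave artefact, but neither removes self-selection on unmeasured motivation, and restricting or adjusting by wave can enlarge the apparent odds ratio.

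The cost is fewer women and a wider interval. Without allowance for clustering, the PHA difference detectable with 80% power is about 26–28 percentage points for 44 against 56 women, and about 35–37 points for 28 against 28 in Waves 2–3, before step 1 reduces the numbers further. No new data collection is needed.
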